# Table 14.2.3.3Proportion of Patients Achieving Sitting BP Goal ( $\leq$ 130/80 mmHg) at Visits 2, 3, and 4(Full Analysis Set and Efficacy Population)

			All Patients
Therapy Type	Visit	Statistic [1,2,3]	(N=xx)
Monotherapy	Visit 2	n/N (Proportion %)	xx/xx (xx.x)
		95% CI	(xx.x, xx.x)
Combined Therapy	Visit 3	n/N (Proportion %)	xx/xx (xx.x)
		95% CI	(xx.x, xx.x)
	Visit 4	n/N (Proportion %)	xx/xx (xx.x)
		95% CI	(xx.x, xx.x)

Note: The Monotherapy analysis (Visit 2) is performed on the Full Analysis Set. The Combined Therapy analysis (Visits 3 and 4) are performed on the Efficacy Population.

[1] A patient is considered to have met the Blood Pressure (BP) goal (controlled BP) if their SBP  $\leq$  130 mmHg AND their DBP  $\leq$  80 mmHg.

[2] n = number of patients who have achieved sitting BP goal at that visit. N = number of patients with data at that visit, regardless of BP goal status.

[3] CI = Confidence Interval.

Source: Listing 16.2.6

Program Name: XXXX.SAS

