extemporaneous combination for additional 4 weeks \pm 2 days, while uncontrolled patients (sitting SBP/DBP >130/80 mmHg) will be up-titrated from ZOF/AML 30/5 mg to ZOF/AML 30/10 mg for further 4 weeks \pm 2 days.

At Visit 3 patients with SBP/DBP values classified as Grade 3 (SBP \geq 180 or DBP \geq 110 mmHg) hypertension will be withdrawn from the study.

If patients at Visit 3, do not tolerate the extemporaneous combination treatment or they have an adherence range below 80% or superior to 120%, they will be withdrawn from the study. At the end of the assessment period (8 weeks \pm 4 days) at Visit 4, the anti-hypertensive effect of the extemporaneous combination (ZOF/AML 30/5 mg and ZOF/AML 30/10 mg) will be evaluated.

Efforts will be made to achieve 1:1 ratio in the enrolment of patients receiving any ACE-i or allowed CCBs (refer to section Subject Study Phases Duration for allowed CCBs). At Visit 2, a minimum of 45% of uncontrolled patients receiving treatment with ZOF 30 mg or AML 5 mg are required to enter the assessment period, in order to maintain a balance between the 2 treatments during the assessment period.

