10 WITHDRAWAL CRITERIA

Patients are free to discontinue the trial at any time without giving their reasons without losing the right to future medical care. Patients who withdraw from the trial will also be withdrawn from the investigational medicinal product.

Patients who voluntarily withdraw their consent can do so for any of the following reasons:

- Does not want to participate in the study anymore
- Does not permit further collection of personal data

The investigator should make a reasonable effort to understand the primary reason for the patient's decision to withdraw his/her consent and record this information.

Study participants may, at any moment, be withdrawn by the Investigator, if considered appropriate. Patients can be withdrawn for any of, but not limited to, the following reasons:

- If the patient meets an exclusion criterion (newly developed or not previously recognized) that precludes further study participation
- Adverse events: when during the conduct of the study, adverse events occur
 that, in the Investigator's judgement, are of such a nature or severity to
 recommend treatment withdrawal
- Failure to comply with requirements of the protocol including, but not limited to evidence of non-compliance with inclusion/exclusion criteria during the study or patient non-compliance with key study procedures

МЕМАЯНИ	Согр	porate Medical Departmo	ent
Identification Number	Version Number	State	Effective date
FORM-000050125	2.0, CURRENT	Effective	08, Jan 2021

- By request of the patient including explicit withdrawal of patient's consent to participate
- Patient's failure to report to study visits
- Patient's loss to follow-up (for guidance see Section 11)
- Withdrawal by Investigator's judgement: Investigator may choose to withdraw a patient from the study if the Investigator deems it in the best interest of the patient to discontinue.

Patients who satisfy the following criteria will also be withdrawn from the study:

- If at Visit 2 patients have a controlled BP (sitting SBP/DBP ≤130/80 mmHg) or do not tolerate the treatment or have an adherence range below 80% or superior to 120%.
- If at Visit 3 the patients do not tolerate the extemporaneous combination treatment or have an adherence range below 80% or superior to 120%.

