- Patients with abnormal renal function (creatinine clearance <30 mL/min) and/or abnormal liver enzyme parameters (alanine aminotransferase [ALT] or aspartate aminotransferase [AST] level of >2.5 × upper limit of normal [ULN] or total bilirubin level >1.5 × ULN).

If a patient has been withdrawn due to an AE, the Investigator must immediately contact the relevant pharmacovigilance contact (see Safety Data Management section). The reason for patient withdrawal must be well-documented in the Electronic Case Report Form (eCRF). The eCRF should capture the date and specific underlying reason for discontinuation of study product or patient discontinuation/withdrawal. Study treatment must be discontinued, and no further assessment conducted, and the data that would have been collected at subsequent visit will be considered missing. Further attempts to contact the patient are not allowed unless safety findings require communication or follow-up. All effort should be made to complete the assessment prior to study withdrawal. A final evaluation at the time of the patient's study withdrawal should be made as detailed in Early termination visit scheduled assessment.

Patients who discontinue from the study early will complete an early termination visit.

MENARINI	Corporate Medical Department		
	** * ** *	G	77.00 dt 1
Identification Number	Version Number	State	Effective date
FORM-000050125	2.0, CURRENT	Effective	08, Jan 2021

Subjects who prematurely withdrawn from study medication or from the study will not be replaced. These subjects will not be considered lost to follow-up.

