12.3 Analysis Populations

A total of three populations will be used for all summaries and analyses. Study participants who have satisfied the population criteria will be classified in the designated population and will only be included in analyses for which they have available data.

Data analysis will be performed using the following analysis sets.

The Safety Population

The Safety population is defined as all study participants who sign the informed consent, meet all screening criteria, are enrolled, and receive at least one dose of the assigned treatment during the run-in period. This population will be used for safety analyses.

The Efficacy Population

The Efficacy population is defined as all study participants in the Safety population who complete the 4-week run-in period and the Visit 2 blood pressure assessment. This will be population for efficacy analysis.

The Per-Protocol Population

The Per-Protocol (PP) population is defined as all study participants in the Efficacy population who were dosed according to protocol, complete the required study visits, and do not experience any major protocol deviations that may impact the primary efficacy assessment through end of treatment.

HEVARIN	Corporate Medical Department		
Identification Number	Version Number	State	Effective date
FORM-000050125	2.0, CURRENT	Effective	08, Jan 2021

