### 5.3.3 Efficacy Population (EFF)

The Efficacy Population (EFF) is defined as all study participants in the Safety Population who complete the 4-week run-in period and meet continuation criteria at Visit 2 [uncontrolled BP (sitting SBP/DBP > 130/80 mmHg), tolerate treatment, and fall within 80-120% treatment adherence] and have at least one available post baseline primary efficacy assessment (from Visit 3 or 4). This population will be used for efficacy analyses.

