### 7.3.2 Proportion of Patients (Endpoints 2.3 and 2.4)

**Endpoint 2.3**: Monotherapy: Number and proportion of patients achieving the BP goal (sitting BP $\leq$ 130/80 mmHg) at Visit 2 (Week 0). Combination therapy: number and proportion of patients achieving the BP goal (sitting BP $\leq$ 130/80 mmHg) at Visit 3 (Week 4) and Visit 4 (Week 8).

**Endpoint 2.4**: Adherence to the treatments (% of doses taken/doses to be taken) at Visit 2 (Week 0), Visit 3 (Week 4) and Visit 4 (Week 8).

Endpoints 2.3 and 2.4 will be analyzed using a 95% binomial confidence interval (CI) for each visit.

A patient who has taken at least 80% and no more than 120% of the required study medication since the last visit will be considered as compliant. Treatment adherence will be summarized incrementally rather than cumulatively so that changes in adherence over time can be accurately reflected. That is, a patient can be compliant between Visits 2 and 3, but non-compliant between Visits 3 and 4, or vice versa.

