### 8.1.2 Treatment Exposure by Visit

At Visit 1 (Week -4), patients on current treatment with AML 5 mg or approved CCBs (see section 4.2 for list of approved CCBs) are provided with 1 box of AML 5 mg for the 4-week run-in period. Patients on current treatment with ZOF 30 mg or other ACE-i are provided with 1 box of ZOF 30 mg for the 4-week run-in period.

At Visit 2 (Week 0), patients with uncontrolled BP (> 130/80 mmHg) will be provided with 1 box of ZOF 30 and 1 box of AML 5 mg while the following patients will be withdrawn from the study:

- Controlled BP (≤ 130/80 mmHg)
- Grade 3 Hypertension (SBP ≥ 180 mmHg or DBP ≥ 110 mmHg)
- Does not tolerate the treatment
- Treatment adherence below 80% or above 120%

At Visit 3 (Week 4), patients with controlled BP ( $\leq$  130/80 mmHg) will continue with ZOF 30 and AML 5 mg (receiving 1 box of each), patients with uncontrolled BP (> 130/80 mmHg) will be up-titrated to ZOF 30 and AML 10 mg (receiving 1 box of each), and the following patients will be withdrawn from the study:

- Grade 3 Hypertension (SBP ≥ 180 mmHg or DBP ≥ 110 mmHg)
- Does not tolerate the treatment
- Treatment adherence below 80% or above 120%

At Visit 4 (Week 8), the anti-hypertensive effect of the extemporaneous combination (ZOF/AML 30/5 mg and ZOF/AML 30/10 mg) will be evaluated.

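### Endpoint 2.3: the Visit 4 BP-goal rate is taken over observed cases, so patients withdrawn at Visit 3 can drop out of it, and no supplementary rate is planned to show the effect

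*SAP*

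**What the plan says.** Endpoint 2.3 on combination therapy is the number and proportion of EFF patients at goal (SBP at most 130 and DBP at most 80 mmHg, SAP 7.1.1) at Visits 3 and 4. The method in SAP 7.3.2 is one line: "Endpoints 2.3 and 2.4 will be analyzed using a 95% binomial confidence interval (CI) for each visit". Footnote 2 of the Table 14.2.3.3 shell sets the denominator: "N = number of patients with data at that visit, regardless of BP goal status". This follows Protocol 12.3, where participants "will only be included in analyses for which they have available data".

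To be in EFF (SAP 5.3.3) a patient who met the Visit 2 continuation criteria must "have at least one available post baseline primary efficacy assessment (from Visit 3 or 4"). A Visit 3 reading alone is therefore enough.

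The Protocol Section 5 rule that opens "At Visit 3 patients with SBP/DBP values classified as Grade 3" ends in withdrawal from the study. SAP 8.1.2 says the same for Visit 3, "and the following patients will be withdrawn from the study", and lists Grade 3 BP, intolerance and adherence below 80% or above 120%. After withdrawal, Protocol Section 10 says "the data that would have been collected at subsequent visit will be considered missing".

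LOCF (SAP 5.6.1) and the per-protocol, site, gender and age repeats (SAP 7.2.2) are sensitivity analyses of Endpoint 1.1 only. SAP 5.6.1 rules out other standard imputation of efficacy data.

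**The concern.** A patient with Grade 3 BP at Visit 3 has SBP of 180 or more, or DBP of 110 or more. That is at least 50 mmHg above the systolic limit of the goal or 30 mmHg above the diastolic limit. The protocol withdraws this patient because of the variable that defines the endpoint, so a certain non-achiever at Visit 3 need not appear in the Visit 4 denominator. Week 8 status is then unobserved.

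The rate carries some weight. The trial has a single treatment path and no comparator arm in which similar losses might offset. The protocol synopsis uses the 95% CI to judge whether the rate at Weeks 4 and 8 differs from Week 0, and SAP 5.9 has the secondary endpoints support the primary conclusion. Selective loss would move the headline control rate with nothing beside it to show by how much.

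**Working it through.** **Tracing one patient.** Take a patient who enters the assessment period, has a BP at Visit 3 and is withdrawn there.

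- EFF: included, because a Visit 3 BP qualifies (SAP 5.3.3).
- Visit 3 rate: included, at goal or not.
- Visit 4 rate: not included if Visit 4 BP is missing (Protocol Section 10; Table 14.2.3.3 footnote 2).
- Early termination: Protocol 2.2 asks for a visit with all the Visit 4 assessments, and Protocol Section 10 also asks for an early termination visit. SAP 5.2.4 tabulates data under the visit recorded in the eCRF and puts early termination visits in summary tables. Table 14.2.3.3 has no row for them and no rule maps them to Visit 4. Whether such a BP enters N at Visit 4 is open.
- A patient with no post-baseline BP is outside EFF and in neither rate.

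**Inputs.** The documents state no expected goal rate and no withdrawal rate after Visit 2, so the plan has no figure for this endpoint to reproduce. The base used is the 216 patients planned to start the assessment period (Protocol Section 5). As a sample size, 216 reproduces with a one-sample t-test of 4 against 2 mmHg, SD 10, one-sided 5% (power 90.1%); it has no other role here. The 25% allowance is not a usable loss rate, because Protocol Section 5 places the fall from 290 to 216 before the assessment period. The observed rate p and the number lost k below are assumptions.

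**Formula.** If leavers would reach goal at rate q, the overstatement is p - [p(216 - k) + qk]/216 = (p - q) × k/216. The maximum, at q = 0, is p × k/216. It halves at q = p/2, is zero at q = p, and changes sign if q exceeds p.

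| Lost, k | Share of 216 | Maximum at p = 30% | at p = 40% | at p = 60% |
|---|---|---|---|---|
| 4 | 1.9% | 0.56 points | 0.74 | 1.11 |
| 11 | 5.1% | 1.53 | 2.04 | 3.06 |
| 22 | 10.2% | 3.06 | 4.07 | 6.11 |

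Grade 3 leavers alone, k = 1 to 3: from 0.30 × 1/216 = 0.14 points to 0.60 × 3/216 = 0.83 points.

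**Worked example (all counts assumed).** 216 enter; 2 have no post-baseline BP, so EFF = 214; 9 leave at Visit 3, 3 of them at goal then; 205 have Visit 4 data and 82 are at goal. Intervals are exact (Clopper-Pearson), since the SAP does not name a binomial method.

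- Observed cases: 82/205 = 40.0% (33.2 to 47.1).
- Missing as not at goal, EFF: 82/214 = 38.3% (31.8 to 45.2).
- Missing as not at goal, all entrants: 82/216 = 38.0% (31.5 to 44.8).
- Visit 3 status carried forward, EFF: (82 + 3)/214 = 39.7% (33.1 to 46.6).
- Opposite extreme, all 11 at goal: 93/216 = 43.1% (36.4 to 49.9).

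The CI half-width is (47.1 - 33.2)/2, about 7 points.

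**The case against.** The strongest reply is that the denominator is an openly declared observed-case choice for a supportive, descriptive endpoint, and that nothing in the documents requires a non-responder rate. That stands: this is a missing supplement, not an oversight or an error.

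A reader might infer that the effect cannot be bounded from the planned output. The documents do not support that. The numerator in Table 14.2.3.3 over the EFF count in Table 14.1.2 gives the missing-as-not-at-goal rate. Carry-forward status can be counted from Listing 16.2.6, which shows goal status by patient and visit and marks LOCF values. The rate over all entrants is less clean. The Table 14.1.2 line for patients who did not complete Visit 3 or 4 would supply the extra count. But the continuation criteria in SAP 5.3.3 do not name Grade 3 BP, so patients withdrawn for it at Visit 2 could fall on the same line. What remains is that none of these rates is a planned summary result with a CI.

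A reader might also infer that the primary analysis escapes this loss. It does not: the paired Visit 2 to Visit 4 t-test (SAP 7.2.1) loses the same leavers. The difference is that it has an LOCF check and Endpoint 2.3 has none.

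**Conclusion.** The point holds as a cheap improvement. The Visit 4 goal rate can lose patients whom the protocol withdraws because of their BP, and no supplementary rate or sensitivity analysis is planned for Endpoint 2.3. Grade 3 leavers push the observed rate up. For those withdrawn for intolerance or adherence the direction is not established.

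The size rests wholly on assumed losses of 2-10% and observed rates of 30-60%: at most about 0.6 to 6 points, and under 1 point from one to three Grade 3 leavers. In the worked example the lower-bound and carry-forward rates lie 0.3 to 2.0 points below the observed rate, well inside the CI half-width.

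A reader might infer that the Week 8 control rate will be materially overstated. The documents do not show that, because they give neither a withdrawal rate after Visit 2 nor the goal status of leavers, and early-termination readings might return some of them to N.

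**What to change.** Keep the observed-case rate as planned, and pre-specify before database lock:

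1. In Table 14.2.3.3, a Visit 4 rate over all EFF patients, ideally all who entered the assessment period, with missing or withdrawn counted as not at goal, a 95% CI, and the label of a conservative lower bound.
2. Optionally, a Visit 4 row in EFF with Visit 3 goal status carried forward, in line with the LOCF already planned for the primary endpoint.
3. One sentence stating whether an early-termination BP counts as Visit 4 in the observed-case rate.

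As a separate minor item, the withdrawal lists need reconciling. Protocol Section 5 and SAP 8.1.2 name Grade 3 BP as a reason at Visits 2 and 3. The list in Protocol Section 10 does not: its Visit 3 entry, "If at Visit 3 the patients do not tolerate the extemporaneous combination treatment", goes on only to adherence. Footnotes 2 and 3 of Table 14.1.1 follow Section 10. Once the passages agree, withdrawals for Grade 3 BP should appear under a named reason.

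The cost is one or two extra rows and some footnote wording, from data already collected. The primary test, EFF and the models for Endpoints 3.3 and 3.4 stay as they are. The downside is that the lower-bound rate is conservative, because some leavers may have been at goal.

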#### Table 14.2.3.4 Proportion of Patients with 80% - 120% Adherence to Treatment at Visits 2, 3, and 4 (Full Analysis Set and Efficacy Population)

			All Pati (N=x	ents x)
Therapy Type	Visit	Statistic [1,2]	eCRF-Reported Adherence	Derived Adherence
Monotherapy	Visit 2	n/N (Proportion %)	xx/xx (xx.x)	xx/xx (xx.x)
		95% CI	(xx.x, xx.x)	(xx.x, xx.x)
Combined Therapy	Visit 3	n/N (Proportion %)	xx/xx (xx.x)	xx/xx (xx.x)
		95% CI	(xx.x, xx.x)	(xx.x, xx.x)
	Visit 4	n/N (Proportion %)	xx/xx (xx.x)	xx/xx (xx.x)
		95% CI	(xx.x, xx.x)	(xx.x, xx.x)

Note: The Monotherapy analysis (Visit 2) is performed on the Full Analysis Set. The Combined Therapy analysis (Visits 3 and 4) are performed on the Efficacy Population.

[1] n = number of patients who met 80% - 120% adherence to treatment at that visit. N = number of patients with data at that visit, regardless of treatment adherence status.

[2] CI = Confidence Interval.

Source: Listing 16.2.5.1

Program Name: XXXX.SAS

## Table 14.2.4.1 Difference in Mean Change for Sitting Systolic (SBP) and Diastolic Blood Pressure (DBP) From Visit 1 to Visits 2, 3, and 4 (Full Analysis Set and Efficacy Population)

				SBP		DBP		
			-	ZOF/AML [4]	ACE-i/CCB [5]	ZOF/AML [4]	ACE-i/CCB [5]	
Therapy Type	Visit [1]	Statistic Type [2,3]	Statistic	(N=xx)	(N=xx)	(N=xx)	(N=xx)	
Monotherapy	Visit 2 CFS	MMRM	n	ХХ	XX	XX	ХХ	
			LSM (SE)	xx.x (xx.xxx)	xx.x (xx.xxx)	xx.x (xx.xxx)	xx.x (xx.xxx)	
			95% CI	(xx.x, xx.x)	(xx.x, xx.x)	(xx.x, xx.x)	(xx.x, xx.x)	
		v. ACE-i/CCB	LSM Difference (SE)	xx		xx		
			95% CI	xx.x (xx.xxx)		xx.x (xx.xxx)		
			p-value	x.xxx		x.xxx		
Combined Therapy	Visit 3 CFB	MMRM	n	xx	xx	xx	xx	
			LSM (SE)	xx.x (xx.xxx)	xx.x (xx.xxx)	xx.x (xx.xxx)	xx.x (xx.xxx)	
			95% CI	(xx.x, xx.x)	(xx.x, xx.x)	(xx.x, xx.x)	(xx.x, xx.x)	
		v. ACE-i/CCB	LSM Difference (SE)	xx		xx		
			95% CI	xx.x (xx.xxx)		xx.x (xx.xxx)		
			p-value	x.xxx		x.xxx		
	Visit 4 CFB	MMRM	n	xx	xx	xx	xx	
			LSM (SE)	xx.x (xx.xxx)	xx.x (xx.xxx)	xx.x (xx.xxx)	xx.x (xx.xxx)	
			95% CI	(xx.x, xx.x)	(xx.x, xx.x)	(xx.x, xx.x)	(xx.x, xx.x)	
		v. ACE-i/CCB	LSM Difference (SE)	xx		xx		
			95% CI	xx.x (xx.xxx)		xx.x (xx.xxx)		
			p-value	x.xxx		x.xxx		

Note: The Monotherapy analysis (Visit 2) is performed on the Full Analysis Set. The Combined Therapy analysis (Visits 3 and 4) are performed on the Efficacy Population. [1] CFS = Change from Screening (Visit 1). CFB = Change from Baseline (Visit 2).

[2] MMRM = Mixed Model Repeated Measures.

[3] A separate model is used for the monotherapy and combined therapy analyses. The models use an unstructured covariance matrix; change from screening (monotherapy) or baseline (combined therapy) for SBP/DBP as the response variable; visit, treatment subgroup, visit\*treatment subgroup interaction, and screening (monotherapy) or baseline (combined therapy) SBP/DBP as covariates; and a random effect for patient.

[4] ZOF/AML subgroup: Patients who were on ZOF 30 mg or AML 5 mg at Visit 1 (Week -4) and continued on same therapies.

[5] ACE-i/CCB subgroup: Patients who switched to ZOF 30 mg or AML 5 mg from any other ACE-i or CCBs at Visit 1 (Week -4).

Source: Listing 16.2.6

Program Name: XXXX.SAS

Programming Note:

• If a different covariance structure is used in case of model nonconvergence, footnote 3 should be updated accordingly.

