### 3.1.3 Exploratory Objectives

- **Objective 3.1**: To assess change in mean sitting SBP and DBP between Visit 1 (Week -4) and Visit 2 (Week 0), Visit 3 (Week 4) and Visit 4 (Week 8).
- **Objective 3.2**: To assess the antihypertensive efficacy at different time points in patients who (1) received ZOF or AML monotherapies before the run-in period, (2) received any other ACE-i or CCB monotherapies before the run-in period.

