### 3.2.3 Exploratory Endpoints

- Endpoint 3.1: Change in mean sitting SBP and DBP between Visit 1 (week -4) and Visit 2 (Week 0), visit 3 (Week 4) and Visit 4 (Week 8):
  - In the group of patients who were on ZOF 30 mg and AML 5 mg at Visit 1 (Week -4) and continued the same therapies.

- In the group of patients who switched to ZOF 30 mg or AML 5 mg from any other ACE-i or CCBs at Visit 1 (Week -4).
- Endpoint 3.2: Change in mean sitting SBP and DBP for uncontrolled patients at Visit 3 (Week 4), between Visit 2 (Week 0) and Visit 3 (Week 4).
  - In the group of patients who were on ZOF 30 mg and AML 5 mg at Visit 1 (Week -4) and continued the same therapies.
  - In the group of patients who switched to ZOF 30 mg or AML 5 mg from any other ACE-i or CCBs at Visit 1 (Week -4).
- Endpoint 3.3:
  - Monotherapy: number and proportion of patients achieving the BP goal (sitting BP≤130/80 mmHg) at Visit 2 (Week 0):
    - In the group of patients who were on ZOF 30 mg and AML 5 mg at Visit 1 (Week -4) and continued the same therapies.
    - In the group of patients who switched to ZOF 30 mg or AML 5 mg from any other ACE-i or CCBs at Visit 1 (Week -4).
  - Combination therapy: number and proportion of patients achieving the BP goal (sitting BP≤130/80 mmHg) at Visit 3 (Week 4):
    - In the group of patients who were on ZOF 30 mg and AML 5 mg at Visit 1 (Week -4) and continued the same therapies.
    - In the group of patients who switched to ZOF 30 mg or AML 5 mg from any other ACE-i or CCBs at Visit 1 (Week -4).

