### 5.2 Study Variables

### 5.2.1 Baseline

Patients are instructed to take the study treatment after all visit evaluations have been performed on scheduled visit days. Assessments performed at Visit 2 will be considered Baseline since the first dose combination therapy (ZOF/AML) occurs after the completion of Visit 2 assessments. For assessments performed at Visit 1 and not Visit 2 (e.g., laboratory and ECG assessments), the Visit 1 assessment will be considered Baseline.

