### 7.4.1 Mean Change (Endpoints 3.1 and 3.2)

**Endpoint 3.1**: Change in mean sitting SBP and DBP between Visit 1 (Week -4) and Visit 2 (Week 0), Visit 3 (Week 4) and Visit 4 (Week 8).

**Endpoint 3.2**: Change in mean sitting SBP and DBP for uncontrolled patients at Visit 3 (Week 4), between Visit 2 (Week 0) and Visit 3 (Week 4).

Endpoints 3.1 and 3.2 will be analyzed using mixed models for repeated measured (MMRM) to assess the mean change in SBP and DBP. The models will be built as follows:

- Endpoint 3.1
  - *Response* = change from screening BP
  - *Covariates* = treatment subgroup, study visit, treatment subgroup-by-visit interaction, screening BP values
  - *Random effect* = patient
  - Covariance matrix = unstructured
    - In the event of lack of model convergence, other covariance structures may be used.
    - If all MMRM fail to converge, this endpoint will be analyzed as described in section 7.4.1.1 below.
- Endpoint 3.2
  - *Response* = change from baseline BP

- *Covariates* = treatment subgroup, study visit, treatment subgroup-by-visit interaction, baseline BP values
- *Random effect* = patient
- *Covariance matrix* = unstructured
  - In the event of lack of model convergence, other covariance structures may be used.
  - If all MMRM fail to converge, this endpoint will be analyzed as described in section 7.4.1.1 below.

Least-squares (LS) means, standard error (SE), and 95% CIs for mean change from screening/baseline for BP will be presented by visit and treatment subgroup. The LS-means difference, SE, 95% CI, and two-sided p-value for the difference between treatment subgroups in mean change from screening/baseline for sitting SBP and DBP will be presented where a p-value of  $\leq$  0.05 indicates a significant difference between groups.

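### Exploratory endpoint 3.1 is change from Visit 1 in the SAP text, but its table shell (Table 14.2.4.1) models Visits 3 and 4 as change from Visit 2

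*SAP*

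**What the plan says.** Objective 3.1 in SAP section 3.1.3 is "To assess change in mean sitting SBP and DBP between Visit 1 (Week -4) and Visit 2 (Week 0"), and then to Visits 3 and 4. Endpoint 3.1 in section 3.2.3 keeps that reference visit: "Change in mean sitting SBP and DBP between Visit 1 (week -4) and Visit 2 (Week 0), visit 3 (Week 4) and Visit 4". It is reported separately for patients who continued zofenopril or amlodipine at Visit 1 and for those switched from another drug of the class. Protocol section 4 also takes Visit 1 as the starting point.

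Section 7.4.1 gives the endpoint 3.1 model. The response is "change from screening BP" and the covariates are "treatment subgroup, study visit, treatment subgroup-by-visit interaction, screening BP values". The next bullet uses change from baseline, with baseline BP as covariate, for endpoint 3.2 only. Section 5.2.1 fixes what baseline means for BP: "Assessments performed at Visit 2 will be considered Baseline".

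The shell list assigns Table 14.2.4.1 to endpoint 3.1. The table is titled "Difference in Mean Change for Sitting Systolic (SBP) and Diastolic Blood Pressure (DBP) From Visit 1 to Visits 2, 3, and 4". Its rows, however, are Visit 2 CFS, Visit 3 CFB and Visit 4 CFB. Footnote 1 defines CFS as change from Visit 1 and CFB as change from Visit 2. Footnote 3 calls for separate monotherapy and combined-therapy models, with "change from screening (monotherapy) or baseline (combined therapy) for SBP/DBP as the response variable" and the matching screening or baseline BP as covariate. A note assigns the Visit 2 row to the FAS and the Visit 3 and 4 rows to the EFF population.

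**The concern.** The section 7.4.1 model and the shell model are different analyses with different response variables and covariates. Only the Visit 2 row of the shell matches the endpoint. Under the shell, the Visit 3 and Visit 4 figures would measure what happened after combination therapy began, yet would appear under a title that promises change since screening.

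The reference visit matters for this comparison because switched patients changed drug at Visit 1. Any run-in difference between continued and switched patients belongs to the endpoint as defined. Measuring from Visit 2, and adjusting for Visit 2 BP, takes part of that difference out of the later rows.

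**Working it through.** The plan states no figure for endpoint 3.1, so there is none to reproduce. The check sets the texts side by side and then asks whether the two rules could give the same answer.

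**1. The texts**

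| Item | SAP 3.2.3 and 7.4.1 | Shell, Table 14.2.4.1 |
|---|---|---|
| Reference, Visit 2 row | Visit 1 | Visit 1 |
| Reference, Visit 3 and 4 rows | Visit 1 | Visit 2 (title says Visit 1) |
| Covariate, Visit 3 and 4 rows | screening BP | Visit 2 BP |
| Models | one, across visits | two, split by therapy period |

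The row labels, footnote 1 and footnote 3 agree with one another, so this is not a single typing slip. Section 10.1 declares only population changes, and 10.2 only the subgroups for endpoint 3.2. Section 11 lets shells change in layout or formatting without a SAP change; a new response variable is neither.

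**2. Raw means.** For the same patients, (V4 − V1) = (V4 − V2) + (V2 − V1), and likewise for Visit 3. The two versions agree only if the mean run-in change, V2 − V1, is zero.

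**3. Adjusted contrast, continued minus switched.** Assume equal SDs, a common within-patient correlation r, equal Visit 1 means, and a run-in difference D that persists to Visit 3. The within-group slope of the change on the earlier value is then r − 1.

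- From Visit 1, adjusted for Visit 1: (D − 0) − (r − 1) × 0 = D.
- From Visit 2, adjusted for Visit 2: (D − D) − (r − 1) × D = (1 − r)D.

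For r from 0.3 to 0.7 the second version gives 0.7D to 0.3D.

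**4. Simulation of step 3.** Assumed values: 200,000 patients, SD 8 mmHg, r = 0.5, and a further fall of 4 mmHg from Visit 2 to Visit 3 in both groups. Results are in mmHg.

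| Run-in fall, continued / switched | D | Contrast from Visit 1 | Contrast from Visit 2 |
|---|---|---|---|
| 0 / 0 | 0 | 0.03 | 0.03 |
| 0 / 2 | 2 | 2.05 | 1.03 |
| 0 / 3 | 3 | 2.96 | 1.46 |
| 0 / 5 | 5 | 4.99 | 2.49 |
| 2 / 5 | 3 | 3.01 | 1.53 |

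The last column agrees with (1 − 0.5)D.

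**5. LS means.** In the 2 / 5 case the continued group's LS mean is −6.03 from Visit 1 and −3.24 from Visit 2, a gap of 2.79 against a run-in fall of 2. For the switched group the figures are −9.03 and −4.77, a gap of 4.26 against a run-in fall of 5. The raw-mean identity does not carry over to LS means, because the covariate changes too.

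**6. Recovery from other output.** Tables 14.2.1.1 and 14.2.1.2 report by combination dose, with change from Visit 2. Table 14.2.4.2 covers only Visit 2 to Visit 3 in uncontrolled patients. Adding the Visit 2 row of Table 14.2.4.1 to a later row fails because the populations and covariates differ. Only the by-patient listing (16.2.6) holds the values needed.

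**The case against.** Nothing in the documents says that a shell overrides SAP text. The shells are dated 16 May 2022 and SAP version 2.0 is dated 23 May 2022, with a history entry about clarifying endpoints and analysis methods. If the programmers follow section 7.4.1, the fault is confined to row labels and footnotes. The rows are also openly labelled CFS or CFB, so a careful reader would see the reference point despite the title. This stands: the consequence depends on which text is followed. The need to reconcile them does not.

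The shell's choice also has a possible source. Protocol section 12.5.5 describes the exploratory BP models as change from baseline with a baseline covariate. But the protocol's own endpoint starts at Visit 1, and section 7.4.1 is explicit, so this may explain the shell without settling the matter.

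A reader might infer that every reported fall at Visits 3 and 4 will be too small by exactly the run-in change. The documents do not support that. The identity holds for raw means on the same patients, whereas the table reports LS means with a different covariate. The direction is not known either. Continuers stay on the same drug and dose during run-in, and the EFF population requires BP still uncontrolled at Visit 2, which excludes patients who reached the goal during run-in. A mean run-in change near zero, or a small rise, is plausible.

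A reader might also infer that the shell removes the run-in difference from the later rows altogether. Under the assumptions in the working it attenuates the contrast and leaves (1−r)D.

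**Conclusion.** The inconsistency is real and undeclared. Sections 3.2.3 and 7.4.1 and the table title use Visit 1; the row labels and footnotes 1 and 3 use Visit 2 for Visits 3 and 4. Following the shell would put a different quantity under a title that names Visit 1, and no other summary table supplies the stated endpoint.

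Its size cannot be fixed from the documents, which give no run-in change, SD by visit or between-visit correlation. Raw means would differ by the mean run-in change, of unknown sign and possibly near zero. The adjusted contrast would be about (1−r)D instead of D if SDs and Visit 1 means are equal, the correlation is common and the run-in difference persists. The simulation also ignores the EFF selection at Visit 2, so its figures are illustrations only.

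The impact is limited to one exploratory comparison of non-randomised subgroups. The primary and secondary analyses do not use this table.

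**What to change.** Relabel the Visit 3 and Visit 4 rows of Table 14.2.4.1 as CFS. Reword footnote 3 so that the response is change from screening with screening BP as covariate at every visit, as in section 7.4.1.

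Settle the population at the same time. Section 7 defaults to EFF and names FAS only for the Visit 2 BP-goal analysis, while the shell uses FAS for the Visit 2 row here as well. Either keep separate FAS (Visit 2) and EFF (Visits 3 and 4) models or fit one model on one population, and state the choice in sections 7 and 7.4.1. If the models stay separate, drop the visit and visit-by-subgroup terms from the Visit 2 model: with a single post-screening visit they cannot be estimated.

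Put any change-from-Visit-2 analysis in a separately titled table. If Visit 2 is the intended reference, amend endpoint 3.1, section 7.4.1 and the table title instead, and declare the change in section 10.

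The cost is two row labels, a footnote, a model statement and a sentence or two of SAP text. No new data are needed.
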